2.5 GROUP-LEVEL UNBLINDING

Group-level unblinded (VGX-3100, Placebo) summaries and analyses of efficacy will be produced once the primary endpoint Week 36 visit data are completed for all subjects; subject-level blinding will be maintained. Long-term follow-up data will continue to be collected for all subjects with remaining visits through the final Week 88 visit. The summaries and analyses will allow the Sponsor to have results with respect to the primary endpoint and all other efficacy endpoints corresponding to the cervix and the Week 36 visit on which to make decisions regarding the VGX-3100 program, while still gathering secondary and exploratory endpoint and safety data through the final Week 88 visit. The planned set of summaries and analyses is comprised of a) the primary composite endpoint of histopathologic regression and virologic clearance, b) the secondary endpoint of histopathologic regression, c) the secondary endpoint of virologic clearance, d) the secondary composite endpoint of histopathologic regression to normal and virologic clearance, e) the secondary endpoint of histopathologic regression to normal, and f) the secondary endpoint of histopathologic non-progression. None of these summaries or analyses will be provided if the total count of subjects who experience the event of interest is greater than 0 and the count for any treatment group relative to this total count is less than 3% for a given summary/analysis. Also, items a) through f) are planned to be produced in the order in which they are listed, but as there are intersecting endpoints among these items, items among b) through f) will not be produced if the difference in total count of subjects who experience the event of interest is greater than 0 and the count for any treatment group is 0, relative to any preceding item in the set. The group-level unblinded (VGX-3100, Placebo) production of the summaries and analyses will not include anyone directly involved with the trial or any additional unblinded personnel; only the external Contract Research Organization (CRO), PPD, which has already been providing unblinded summaries for the Data Safety Monitoring Board, will be utilized. Thus, the trial will remain blinded with respect to subject treatment assignment throughout the trial.

3 HYPOTHESIS AND STUDY OBJECTIVES

3.1 HYPOTHESIS

Three 6 mg doses of VGX-3100 (DNA Plasmids encoding E6 and E7 proteins of HPV-16 and HPV-18) delivered IM followed by EP with CELLECTRATM 5PSP to adult women with histologically

confirmed HSIL of the cervix, associated with HPV-16 and/or HPV-18 will result in a higher percentage of women with histopathological regression of cervical HSIL lesions to no evidence of cervical HSIL and virologic clearance of HPV-16/18 compared to placebo delivered IM followed by EP with CELLECTRATM 5PSP at the Week 36 visit.⁴

3.2 PRIMARY OBJECTIVE AND ENDPOINT

Objective	Endpoint
compared with placebo with respect to combined histopathologic regression of	Proportion of subjects with no evidence of cervical HSIL on histology (i.e. biopsy or excisional treatment) and no evidence of HPV-16 and/or HPV-18 in cervical samples by type specific HPV testing at Week 36 visit

⁴ The time frame is defined as any time starting from 14 days prior to the protocol-specified target date of Week 36.

3.3 SECONDARY OBJECTIVES AND ASSOCIATED ENDPOINTS

Secondary Objectives	Associated Secondary Endpoints
1. Evaluate the safety and tolerability of	1a. Incidence and severity of local and systemic
VGX-3100 delivered IM followed by EP	events for 7 and 28 days following each
with CELLECTRA [™] 5PSP	investigational treatment and for the duration of
	the study (through Week 88 visit)
	1b. Incidence and severity of all adverse events
	including SAEs (e.g. SUSAR, UADE and other
	unexpected AEs) for the duration of the study
	(through Week 88 visit)
2.Determine VGX-3100 efficacy compared	2. Proportion of subjects with no evidence of
to placebo as measured by histopathologic	cervical HSIL on histology (i.e. biopsies or
regression of cervical HSIL	excisional treatment) at Week 36 visit
3.Determine VGX-3100 efficacy compared	3. Proportion of subjects with no evidence of HPV-
to placebo as measured by virologic	16 and/or HPV-18 in cervical samples by type
clearance of HPV-16 and/or HPV-18	specific HPV testing at Week 36 visit
4.Determine VGX-3100 efficacy compared	4. Proportion of subjects with no evidence of Low
to placebo as measured by complete	grade squamous intraepithelial lesion (LSIL) or
histopathologic regression of cervical	HSIL (i.e. no evidence of CIN1, CIN2 or CIN3)
HSIL to normal	on histology (i.e. biopsies or excisional
	treatment) at Week 36 visit
5.Determine VGX-3100 efficacy compared	5. Proportion of subjects with no evidence of LSIL
to placebo as measured by both complete	or HSIL (i.e. no evidence of CIN1, CIN2 or CIN3
histopathologic regression of cervical	on biopsies or excisional treatment) on histology
HSIL to normal and virologic clearance of	, -
HPV-16 and/or HPV-18	evidence of HPV-16 and/or HPV-18 by type
	specific HPV testing at Week 36 visit
6.Determine the efficacy of VGX-3100	1 2
compared with placebo as measured by	cervical HSIL to cervical carcinoma from
histopathologic non-progression	baseline on histology (i.e. biopsies or excisional
	treatment) at Week 36 visit
7.Describe the clearance of HPV-16 and/or	
HPV-18 infection from non-cervical	and/or HPV-18 on specimens from non-cervical
anatomic locations	anatomic locations (i oropharynx, vagina and
	intra-anal) at Week 36 Visit
	8a. Levels of serum anti-HPV-16 and anti-HPV-18
immune response to VGX-3100 compared	antibody concentrations at Weeks 15, and 36
with placebo at post dose 3, and Week 36	
visits as assessed relative to baseline	8b. Interferon-γ ELISpot response magnitudes at
	baseline, Weeks 15, and 36 visits
	8c. Flow Cytometry response magnitudes at
	baseline and Week 15 visits

3.4 EXPLORATORY OBJECTIVES AND ASSOCIATED ENDPOINTS

Exploratory Objectives	Associated Endpoints	
Evaluate tissue immune responses to VGX-3100 in cervical samples	1. Assessment of markers including but not limited to CD8+ and FoxP3+ infiltrating cells. Additional assessments may include visualization of Granulysin, Perforin, CD137, CD103 and PD-L1 in cervical tissue as sample allows. Markers listed here may change as new relevant information becomes available	
2. Describe association of microRNA (miRNA) profiles, DNA methylation profile, previous colposcopy, cytology and HPV testing results with Week 36 histologic regression	2. Colposcopy, cytology, and HPV test results (Weeks 8, 15 and 28 visits), miRNA profile (baseline, Week 8) and DNA methylation profile (baseline, Week 15) in conjunction with histologic regression of cervical HSIL at Week 36 visit	
3. Describe the durability of virologic clearance of HPV-16 and/or HPV-18 for subjects treated with VGX-3100 compared with those treated with placebo	3. Proportion of subjects with no evidence of HPV-16 and/or HPV-18 by type specific HPV testing at Weeks 62 and 88 visits	
4. Describe the patient-reported outcomes for subjects treated with VGX-3100	4. Patient-reported outcome questionnaires will be self-administered at baseline, Weeks 4, and 12, 8-14 days following each dose, and at Weeks 28, 36, 40 and 88 by subjects enrolled in US, Canada, Mexico, Germany and UK.	
5. Determine whether a tissue-based score derived using an immunologic markers (Immunoscore) at baseline is predictive for histological and virological response to VGX-3100 at Week 36	6 Immunoscore results for VGX-3100 treated subjects and in conjunction with histological and virological outcomes at Week 36	

4 SELECTION OF SUBJECTS

4.1 INCLUSION CRITERIA

Each subject must meet all of the following criteria to be enrolled in the study:

- 1. Women aged 18 years and above and meets minimum age of consent per local regulations);
- 2. Confirmed cervical infection with HPV types 16 and/or 18 at screening by cobasTM HPV test;
- 3. Cervical tissue specimen/slides provided to Study Pathology Adjudication Committee for diagnosis must be collected within 10 weeks prior to anticipated date of first dose of study drug;
- 4. Histologic evidence of cervical HSIL as confirmed by PAC at screening;
- 5. Must understand, agree and be able to comply with the requirements of the protocol. Subjects must be willing and able to provide voluntary consent to participate and sign a Consent Form prior to study-related activities;

- 6. Must be judged by Investigator to be an appropriate candidate for the protocol-specified procedure (i.e. excision, 4-quadrant biopsy with ECC, or 4-quadrant biopsy) required at Week 36;
- 7. Satisfactory colposcopy at screening, defined as full visualization of the squamo-columnar junction (Type I or II transformation zone) and complete visualization of the upper limit of aceto-white epithelium or suspected CIN disease;
- 8. Cervical lesion that is accessible for sampling by biopsy instrument (e.g. Mini-Tischler device);
- 9. Cervical lesion of adequate size to ensure that a visible lesion remains after screening biopsy;
- 10. Must meet one of the following criteria with respect to their reproductive capacity:
 - a) Is post-menopausal as defined by spontaneous amenorrhea for more than 12 months
 - b) Is surgically sterile due to absence of ovaries or due to a bilateral tubal ligation/occlusion performed more than 12 months prior to screening
 - c) WOCBP is willing to use a contraceptive method with failure rate of less than 1% per year when used consistently and correctly from screening until Week 36. The following methods are acceptable:
 - i. Hormonal contraception: either combined or progestin-alone including oral contraceptives, injectable, implants, vaginal ring, or percutaneous patches. Hormonal contraceptives must not be used in subjects with a history of hypercoagulability (e.g., deep vein thrombosis, pulmonary embolism).
 - ii. Abstinence from penile-vaginal intercourse when this is the subject's preferred and usual lifestyle
 - iii. Intrauterine device or intrauterine system
 - iv. Male partner sterilization at least 6 months prior to the female subject's entry into the study, and this male is the sole partner for that subject
- 11. Normal screening ECG or screening ECG with no clinically significant findings, as judged by the investigator.

4.2 EXCLUSION CRITERIA

Subjects meeting any of the following criteria will be excluded from enrollment in the study:

- 1. Microscopic or gross evidence of adenocarcinoma-in-situ (AIS), high grade vulvar, vaginal (inclusive of cervical HPV-related lesions that extend into the vaginal vault), or anal intraepithelial neoplasia or invasive cancer in any histopathologic specimen at screening;
- 2. Cervical lesion(s) that cannot be fully visualized on colposcopy due to extension high into cervical canal at screening;
- 3. ECC shows a potentially untreated carcinoma, untreated HSIL, indeterminate, or insufficient for diagnosis (ECC is not required to be performed as part of study screening);
- 4. Treatment for cervical HSIL within 4 weeks prior to screening;
- 5. Pregnant, breastfeeding or considering becoming pregnant through Week 36 visit;
- 6. History of previous therapeutic HPV vaccination (licensed prophylactic HPV vaccines are allowed, e.g. GardasilTM, SilgardTM, CervarixTM);
- 7. Presence of any unresolved abnormal clinical screening laboratory values of Grade 1 or greater per CTCAE v 4.03 and deemed clinically significant by the investigator within 45 days prior to Day 0;

- 8. Immunosuppression as a result of underlying illness or treatment including:
 - a) History of or positive serologic test for HIV at screening (performed within 45 days prior to Day 0)
 - b) Primary immunodeficiencies
 - c) Long term use (≥ 7 days) of oral or parenteral glucocorticoids at a dose of ≥20 mg/day of prednisone equivalent; (use of inhaled, otic, and ophthalmic corticosteroids are allowed)
 - d) Current or anticipated use of disease modifying doses of anti-rheumatic drugs (e.g., azathioprine, cyclophosphamide, cyclosporine, methotrexate), and biologic disease modifying drugs such as TNF-α inhibitors (e.g. infliximab, adalimumab or etanercept)
 - e) History of solid organ or bone marrow transplantation
 - f) Any prior history of other clinically significant immunosuppressive or clinically diagnosed autoimmune disease that may jeopardize the safety of the subject or require therapy that would interfere with study assessments or endpoint evaluation, or otherwise impact the validity of the study results.
 - g) Subjects who are malnourished (i.e. medically significant unintentional weight loss, kwashiorkor, or marasmus) based on screening labs, medical history and physical exam per investigator's clinical judgment.
- 9. Receipt of any non-study, non-live vaccine within 2 weeks of dosing;
- 10. Receipt of any non-study, live vaccine (e.g. measles vaccine) within 4 weeks of dosing;
- 11. Current or history of clinically significant, medically unstable disease which, in the judgment of the investigator, would jeopardize the safety of the subject, interfere with study assessments or endpoint evaluation, or otherwise impact the validity of the study results (e.g. chronic renal failure; angina, myocardial ischemia or infarction, class 3 or higher congestive heart failure, cardiomyopathy, or clinically significant arrhythmias);
- 12. Malignancy or systemic treatment for malignancy within 2 years of screening (with the exception of curatively treated, localized anogenital cancers and superficial skin cancers which are allowed);
- 13. Presence of acute or chronic bleeding or clotting disorder that would contraindicate IM injections, or use of blood thinners (e.g. anticoagulants or antiplatelet drugs) within 2 weeks of Day 0;
- 14. History of seizures unless seizure free for 5 years with the use of one or fewer antiepileptic agents;
- 15. Sustained, manually confirmed, sitting systolic blood pressure >150 mm Hg or <90 mm Hg or a diastolic blood pressure >95 mm Hg at Screening or Day 0;
- 16. Resting heart rate <50 bpm (unless attributable to athletic conditioning) or >100 bpm at screening or Day 0;
- 17. Prior major surgery within 4 weeks of Day 0;
- 18. Participation in an interventional study with an investigational compound or device within 30 days of signing informed consent; participation in an observational study is permitted;
- 19. Less than two acceptable sites available for IM injection considering the deltoid and anterolateral quadriceps muscles;
- 20. Tattoos, keloids or hypertrophic scars located within 2 cm of intended treatment site;
- 21. Cardioverter-defibrillator or pacemaker (to prevent a life-threatening arrhythmia) that is located in ipsilateral deltoid injection site (unless deemed acceptable by a cardiologist);

- 22. Metal implants or implantable medical device within the electroporation area;
- 23. Active drug or alcohol use or dependence that, in the opinion of the investigator, would interfere with adherence to study requirements;
- 24. Prisoner or subject who is compulsorily detained (involuntarily incarcerated) for treatment of either a psychiatric or physical (i.e. infectious disease) illness;
- 25. Active military service personnel;
- 26. Study-related staff or family member of study-related staff;
- 27. Any illness or condition that in the opinion of the investigator may affect the safety of the subject or the evaluation of any study endpoint.

4.3 DISCONTINUATION/WITHDRAWAL OF STUDY SUBJECTS

4.3.1 CRITERIA FOR DISCONTINUATION OF INVESTIGATIONAL PRODUCT

Subjects who manifest Grade 4 toxicity attributable to the study treatment will be discontinued from the study treatment. Subjects will not receive further study treatment but will be encouraged to continue follow-up safety assessment through study discharge and not discontinue from the study.

If a subject manifests Grade 3 toxicity attributable to the study treatment, the medical monitor and Investigator will discuss whether further treatment should be continued for that subject.

4.3.2 CRITERIA FOR WITHDRAWAL FROM THE STUDY

All randomized subjects should be encouraged to complete all study treatments and follow-up visits. A subject will be considered to have completed the study when she completes all scheduled study treatments and follow-up visits. However, a subject may voluntarily withdraw from study participation at any time or be withdrawn at any time at the discretion of the investigator for any maternal obstetrical or medical complications after consultation with the medical monitor.

Should a subject fail to attend the clinic for a required study visit, the site should attempt to contact the subject and reschedule the missed visit as soon as possible. The site should also counsel the subject on the importance of maintaining the assigned visit schedule for follow-up and treatment of HSIL (CIN2, CIN3), and ascertain whether or not the subject wishes to and/or should continue in the study based on previous noncompliance. In cases where the subject does not return for the rescheduled visit or cannot be reached to reschedule the missed visit, the site should make every effort to regain contact with the subject (3 telephone calls and if that fails, then a certified letter to the subject's last known mailing address) so that the subject's disposition can be considered as withdrawn from the study (i.e. lost to follow-up). If the contact with subject is re-established, site should contact medical monitor to discuss whether subject can continue study treatment or follow-up visits for the study. For all other subjects withdrawing from the study, an alternative reason for discontinuation should be recorded in the eCRF.

4.3.3 SPONSOR NOTIFICATION OF DISCONTINUATION/ WITHDRAWAL

The investigator or study coordinator must notify the Sponsor within 24 hours if a subject has been discontinued/withdrawn due to an AE. If a subject discontinues from the study or is withdrawn from the study prior to study completion, all applicable activities scheduled for the final study visit should be performed at the time of discontinuation. The investigator will make every effort to have

all scheduled immune assessment blood samples collected as indicated in the Schedule of Events in the synopsis, Table 1. Any AEs and/or SAEs present at the time of discontinuation/withdrawal should be followed in accordance with the safety requirements outlined in section 7.1 – Safety Parameters.

4.3.4 REASON FOR DISCONTINUATION/WITHDRAWAL

The primary reason for a subject discontinuing further dosing or withdrawal from the study itself is to be selected from the following standard categories and recorded on the CRF:

- Adverse Event (Adverse Reaction): Clinical or laboratory events occurred that, in the medical judgment of the investigator for the best interest of the subject, are grounds for discontinuation. This includes serious and non-serious adverse events regardless of relation to study drug.
- Death of subject
- Subject voluntarily withdrew consent: The subject desired to withdraw from further participation in the study in the absence of an investigator-determined medical need to withdraw. If the subject gave a reason for withdrawal, it must be recorded on the CRF. This reason does not allow for further data collection and should not be selected if follow-up data collection of this subject is anticipated by the subject.
- Investigator decision to withdraw the subject from participation: Investigator determined a medical need to withdraw the subject. Investigator must consult the Sponsor's Medical Monitor before withdrawing a subject from participation in the study
- Protocol Violation: The subject's findings or conduct failed to meet the protocol entry criteria or failed to adhere to the protocol requirements (e.g., treatment noncompliance, failure to return for defined number of visits). The violation should be discussed with the Sponsor's Medical Monitor prior to discontinuation of study treatments or study withdrawal.
- Lost to Follow-up: The subject fails to attend study visits and study personnel are unable to contact the subject after repeated attempts including telephone calls, letter sent by certified mail or equivalent.
- Other: The subject was terminated for a reason other than those listed above, such as the termination of the study by the Sponsor.

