8.2 RANDOMIZATION AND BLINDING

Subjects will be randomized (2 VGX-3100:1 Placebo) in a stratified manner according to a) the degree of CIN observed in the biopsy specimens at screening (CIN2 vs. CIN3), b) BMI category

(≤25 vs. >25 kg/m²) on Day 0, and c) age category (<25 years vs. ≥25 years) on Day 0. There will be no pre-determined number of subjects required to be randomized within each stratum. To ensure that milder CIN2 disease is not over-represented in the study, the percentage of subjects enrolled with CIN2 will not exceed 50% of the total enrolled. A group of sequential allocation numbers will be designated for use by each participating country.

The study is double-blinded.

8.3 SAMPLE SIZE/POWER

A sample of 198 subjects will be randomized to receive either 6 mg VGX-3100 or placebo IM followed by EP in a 2:1 ratio. This sample size provides 90% power to declare VGX-3100 superior to placebo, assuming the true proportion of subjects who achieve the primary endpoints is 35% and 14% for VGX-3100 and placebo, respectively. These proportions also incorporate missing data (~10%) classified as non-regressors (failures). The assumptions are based on the Phase 2 study results.

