8.4 ANALYSES POPULATIONS

Analysis populations will include:

- The intention to treat (ITT) population includes all subjects who are randomized. Subjects in this sample will be grouped to treatment arms as randomized. Analysis of the ITT population will be primary for the analysis of efficacy in this study.
- The modified intention to treat (mITT) population includes all subjects who receive at least one dose of Study Treatment and who have the analysis endpoint of interest. Subjects in this sample will be grouped to treatment arms as randomized. Analysis of the mITT population will be considered supportive for the corresponding ITT population for the analysis of efficacy.
- The per-protocol (PP) population comprises subjects who receive all doses of Study Treatments and have no protocol violations and who have the analysis endpoint of interest. Subjects in this sample will be grouped to treatment arms as randomized. Analyses on the PP population will be considered supportive of the corresponding ITT population for the analysis of efficacy. Subjects excluded from the PP population will be identified and documented prior to unblinding of the study database.
- The safety analysis set includes all subjects who receive at least one does of Study Treatment. Subjects will be analyzed as to the treatment they received.

8.5 **SUBJECT DISPOSITION**

Disposition will be summarized by treatment arm for the ITT population and will include the number and percentage randomized, the number and percentage who received each dose and the number who completed the trial. The number and percentage of subjects who discontinued will be summarized overall and by reason. The number in each analysis population will also be presented.

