8.15 MISSING VALUES

Missing data will be considered as non-regressors (failures) for the ITT efficacy analysis. A subject's regression outcome is missing if her CIN grade and HPV clearance at Week 36 cannot be determined. Also, any subject who undergoes an unscheduled excision or biopsy in which tissue sample was obtained after Dose 1 and before Week 36 will be considered a non-regressor regardless of the Week 36 result. Efficacy analyses using the mITT population will be conducted and will serve as sensitivity analyses regarding missing data.

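### Sections 4.3.2 and 4.3.4 allow randomised women to be withdrawn from follow-up for non-compliance or entry-criteria failure, which creates avoidable missing Week 36 results that are scored as failures.

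*Protocol*

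**What the plan says.** All references are to Protocol version 5.0.

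**Withdrawal.** Section 4.3.4 gives one list of reasons that serves both for stopping dosing and for leaving the study. Its Protocol Violation entry covers failed entry criteria, treatment non-compliance and failure to return for visits, and adds: "The violation should be discussed with the Sponsor's Medical Monitor prior to discontinuation of study treatments or study withdrawal". Section 4.3.2 tells the site, after a missed visit, to "ascertain whether or not the subject wishes to and/or should continue in the study based on previous noncompliance". For a woman who had been lost and is back in contact, the "site should contact medical monitor to discuss whether subject can continue study treatment or follow-up visits for the study". The first paragraph of 4.3.2 points the other way. It encourages all randomised women to complete treatment and follow-up, and the only investigator ground it names for withdrawal is obstetric or medical complications, after consulting the medical monitor.

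**Analysis.** Section 8.4: "The intention to treat (ITT) population includes all subjects who are randomized", and this population is primary for efficacy. Section 8.15: "Missing data will be considered as non-regressors (failures) for the ITT efficacy analysis". Section 2.1.3 makes the lack of an acceptable Week 36 histology specimen or HPV sample a non-response.

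**Sample size.** Section 8.3: "A sample of 198 subjects will be randomized", 2:1, with assumed response of "35% and 14% for VGX-3100 and placebo, respectively". It says that these rates already include about 10% missing counted as failures.

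**The concern.** The text does not keep two decisions apart: whether a woman receives more study treatment, and whether she is still followed to Week 36. Where the reason is non-compliance or a late-discovered eligibility failure, a woman who would still attend Week 36 can be taken out of follow-up. Under ITT with missing scored as failure, that decision sets her primary outcome.

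Two things are at stake. Loss that is equal in the two arms shrinks the expected difference and costs power. Loss that is unequal biases the difference, in either direction. An analysis plan can choose how to treat a missing result, but it cannot collect a specimen from a woman the protocol allowed to leave, so this has to be settled in the protocol.

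**Working it through.** **1. Can the result be recovered after withdrawal?** No.
- Section 4.3.3 asks for final-visit activities at withdrawal. The final visit is Week 88 (6.2.13), which has colposcopy, cytology and HPV typing but no scheduled biopsy or excision.
- A biopsy or excision taken after Dose 1 but before the Week 36 time frame would itself make her a failure (2.1.3, 8.9, 8.15).
- The mITT analysis, which 8.15 names as the missing-data sensitivity analysis, requires the endpoint (8.4), so it drops her.

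This concerns only women withdrawn before their Week 36 samples. Later withdrawal leaves the primary endpoint intact.

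**2. The plan's own power.** Inputs from 8.3 and 8.9: n = 132 and 66, rates 0.35 and 0.14, one-sided α = 0.025. With pooled rate p̄ = (2 × 0.35 + 0.14)/3 = 0.28:

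- null SE = √[0.28 × 0.72 × (1/132 + 1/66)] = 0.0677
- alternative SE = √[0.35 × 0.65/132 + 0.14 × 0.86/66] = 0.0596
- power = Φ[(0.21 − 1.96 × 0.0677)/0.0596] = Φ(1.30) = 90.3%

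Exact enumeration of the Miettinen–Nurminen score test gives 90.8%. The stated 90% reproduces.

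**3. Further withdrawal.** The protocol gives no frequency for these withdrawals, so the extra rates below are assumptions. A second assumption is that withdrawn women would have responded like observed women: 0.35/0.90 = 38.9% and 0.14/0.90 = 15.6%. The ITT rate is then the observed rate × (1 − total missing). For 5 extra points in both arms: 0.389 × 0.85 = 33.1% and 0.156 × 0.85 = 13.2%.

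| Extra withdrawal beyond 10% | VGX-3100 | Placebo | Difference (points) | Power, approx. | Power, exact |
|---|---|---|---|---|---|
| none | 35.0% | 14.0% | 21.0 | 90.3% | 90.8% |
| 2 points, both arms | 34.2% | 13.7% | 20.5 | 89.3% | 89.9% |
| 5 points, both arms | 33.1% | 13.2% | 19.8 | 87.8% | 88.4% |
| 10 points, both arms | 31.1% | 12.4% | 18.7 | 84.8% | 85.6% |
| 5 points, VGX-3100 only | 33.1% | 14.0% | 19.1 | 84.4% | 85.2% |
| 10 points, VGX-3100 only | 31.1% | 14.0% | 17.1 | 76.5% | 77.6% |
| 5 points, placebo only | 35.0% | 13.2% | 21.8 | 92.7% | 93.1% |

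In the other direction, cutting total missing from 10% to 5% would raise approximate power to 92.4%.

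**4. Type I error under unequal loss.** With no true effect and an observed rate of 15.6% in both arms, 5 extra points lost on placebo only moves the exact one-sided error from 0.023 to 0.031, and 10 points moves it to 0.043. Scoring missing as failure is therefore not conservative when placebo loses more.

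**5. Is unequal loss shown?** Section 2.1 gives Phase 2b ITT (mITT) rates of 35% (40%) and 14% (15%). If responders are the same women in both analyses, missing is 1 − 35/40 = 12.5% on VGX-3100 and 1 − 14/15 = 6.7% on placebo. Allowing for rounding, the ranges are 10.1% to 14.8% (1 − 35.5/39.5 to 1 − 34.5/40.5) and 0% to 12.9% (1 − 14.5/14.5 to 1 − 13.5/15.5). They overlap, so unequal loss is possible but not established.

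**The case against.** The case on the other side is that 4.3.4 is only a list of reasons to record on the CRF, and that the criteria are in 4.3.2, which favours retention. Requiring a discussion with the medical monitor slows withdrawal down, and 4.3.2 also asks for rescheduling, counselling, three calls and a certified letter. That is fair as to intent. It does not remove the express mention of study withdrawal in 4.3.4, or the wording in 4.3.2 that separates whether a woman should continue from whether she wishes to.

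Several mitigations stand. About 10% missing is already in the planning rates. Section 4.3.5 says supplementation will be considered if more than 10% discontinue before the Week 36 procedures, although that adds women rather than retrieving results. The efficacy time frame (Table 6, 8.9) has no stated upper limit, so a late woman can still supply the endpoint, provided she has not been withdrawn. Women who miss visits are also more likely to lack Week 36 data anyway, so not every such loss is avoidable.

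Three stronger readings are tempting and are not supported:
- **That the protocol directs withdrawal, or that the medical monitor decides it.** Withdrawal is permitted, and the monitor step is a discussion.
- **That painful injections will drive unequal loss.** Both arms receive injection with electroporation. Section 2.3 reports that, among administration-site reactions in Phase 2b, only erythema was statistically more frequent on VGX-3100 (78% vs 57%).
- **That 6.12.2 and 7.1.9 contradict the withdrawal text.** They keep women in safety follow-up after an unscheduled biopsy or a pregnancy. The biopsied women are already non-responders, and pregnancy bars contraindicated procedures, so neither section secures a Week 36 endpoint. Section 4.3.1, which stops dosing after Grade 4 toxicity while encouraging women to stay in the study, is a closer parallel but also speaks of safety assessment.

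**Conclusion.** The point holds as an inconsistency worth correcting. Section 4.3.4 and the later part of 4.3.2 allow withdrawal from follow-up on grounds wider than the one investigator ground that 4.3.2 names, and each woman so withdrawn before her Week 36 samples becomes an unrecoverable ITT failure.

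The size is modest and conditional. Power falls below plan only if total missing exceeds the 10% already allowed for: to about 88% with 5 further points in both arms, or about 85% with 10. Those rates are assumptions, as is equal response in withdrawn and observed women. Bias from unequal withdrawal does not depend on that 10% margin, but nothing in the protocol shows that withdrawal would differ by arm. Confidence is moderate because the frequency of such withdrawals is unknown.

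**What to change.** Reconcile 4.3.2 with 4.3.4 and separate stopping study treatment from leaving the study:
- In 4.3.4, under Protocol Violation, delete *or study withdrawal*.
- In 4.3.2, delete *and/or should*.
- Add a sentence, covering the discussion after re-contact as well, that non-compliance or entry-criteria failure alone is not a ground for ending follow-up, so that randomised women who have not withdrawn consent stay in the scheduled follow-up through the Week 36 assessments.

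Leave unchanged the medical and obstetric ground in 4.3.2, the pregnancy provisions in 7.1.9 and all decisions on dosing. In particular, the new sentence should not be written as an unconditional requirement for tissue collection, which would collide with those provisions.

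The cost is a short text change and a CRF completion note. The one downside is continuing already scheduled visits for women who have not complied.
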